**Document Date**  
**10 May 2025**

# Strategic Daytime Napping Enhances Agility and Lowers Perceived Exertion but Does Not Improve Fatigue Resistance in Adolescent Soccer Players

## DETAILED TRIAL PROTOCOL

### 1. Structured Abstract

**Background and rationale:** Strategic daytime napping (25 min, 45 min) may acutely influence anaerobic performance in team sports via sleepiness-recovery dynamics.

**Objectives and hypotheses:** Primary objective is to test whether nap conditions improve pro-agility performance. Hypothesis: N25 and/or N45 outperform N0 on pro-agility time. Secondary objectives examine effects on RSA, RPE, Hooper wellness, and VAS alertness/sleep quality. Exploratory objective assesses associations of PSQI and POMS with outcomes.

**Design:** Quasi-experimental, repeated-measures crossover with 3 conditions (N0, N25, N45), 48-h washout, afternoon sessions, testing 60 min post-awakening.

**Participants and setting:** Sixteen competitive male soccer players (U17–U19), isolated dark rooms at  $\approx 22^{\circ}\text{C}$ ; standardized field/lab conditions.

**Interventions:** N0, 25-min, 45-min nap opportunities; sleep–wake verification by Visual Analogue Scale; prohibition of visual/stimulating activities; standardized warm-up monitored by Polar H10.

**Primary/secondary outcomes:** Primary: Pro Agility Test time. Secondary: RSA (6 $\times$ 30 m, 20-s recovery), RPE, Hooper Index, VAS. Exploratory: correlations with PSQI/POMS.

**Sample size:** G\*Power 3.1.9.7 for RM-ANOVA ( $\alpha=0.05$ ,  $1-\beta=0.80$ ,  $f=0.30–0.40$ ) indicated  $\geq 12$ ;  $n=16$  recruited.

**Randomization and blinding:** Within-subject random order of conditions; automated timing to reduce measurement bias; assessor blinding not implemented.

**Statistical analysis (summary):** RM-ANOVA with Bonferroni adjustments; assumption checks (Levene, Mauchly, Greenhouse–Geisser); effect sizes ( $\eta^2$ , Cohen’s  $dz$ , 95% CI); Pearson correlations.

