### 2. Objectives and Testable Hypotheses

**Primary objective:** Determine whether agility, perceived exertion and fatigue resistance differs between N0, N25, and N45 conditions.

**Primary hypothesis:** N25 and/or N45 conditions gives better results than N0.

**Secondary objectives:** Assess condition effects on Pro Agility time, RSA metrics (best/mean time, fatigue index), RPE, Hooper Index, and VAS alertness/sleep quality.

**Exploratory objectives:** Examine associations between PSQI/POMS and performance/subjective outcomes.

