### 5.4 Informed Consent

- Written consent from all participants; for those under 18, parental/legal guardian consent obtained.
- Ethics approval: Inonu University Non-Interventional Clinical Research Ethics Committee (Approval No: 2024/5635; Date: 05/03/2024); study conducted in accordance with the Declaration of Helsinki.

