## 8. Sample Size and Justification

- **Software and model:** G\*Power 3.1.9.7; repeated-measures ANOVA (within-subjects, 3 conditions) [24].
- **Parameters:**  $\alpha=0.05$ ,  $1-\beta=0.80$ ; expected effect size  $f=0.30-0.40$  based on prior literature [9,25,26].
- **Result:** Minimum  $\geq 12$ ; **n=16** recruited to accommodate variability and potential attrition.
- **Note:** Crossover design increases power by using each participant as own control [10].

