## 13. Statistical Analysis Plan

- **Software:** SPSS v29.
- **Descriptives:** Mean $\pm$ SD, min–max.
- **Assumption checks:** Normality (skewness/kurtosis within  $\pm 1.5$ ), homogeneity (Levene), sphericity (Mauchly; Greenhouse–Geisser corrections if violated).
- **Primary analysis:** RM-ANOVA across N0–N25–N45; Bonferroni where appropriate.
- **Effect sizes:**  $\eta^2$  (small  $<0.06$ ; medium  $0.06–<0.14$ ; large  $\geq 0.14$ ) and Cohen’s dz for pairwise comparisons; 95% CIs [10,30].
- **Secondary analyses:** RM-ANOVA for RSA metrics, RPE, Hooper, and VAS with appropriate corrections.
- **Exploratory analyses:** Pearson correlations between PSQI/POMS and outcome variables [23].
- **Missing data and sensitivity:** Pre-specified sensitivity checks reported.
- **Pre-specified subgroups:** None; all participants classified as intermediate chronotype (MEQ) [20,28].

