## 17. Timeline and Gantt Plan

- **Preparation (Months 0–1):** Ethics approval, device calibration, staff training, pilot tests.
- **Data collection (Months 2–3):** Three sessions per participant, 48-h washout.
- **Analysis (Months 3–4):** Data cleaning, statistical analyses, sensitivity checks.
- **Reporting (Months 4–5):** Manuscript and supplementary materials.

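### The title states results the plan cannot support on fatigue, and section 2 contradicts sections 1 and 7 on which outcome is primary

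*Protocol*

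**What the plan says.** The title above the protocol says that napping improves agility and reduces exertion, and that it "Does Not Improve Fatigue Resistance in Adolescent Soccer Players". The document is dated 10 May 2025. Section 5.4 gives the ethics clearance as "Approval No: 2024/5635; Date: 05/03/2024".

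On outcomes, section 2 sets the primary objective as: "Determine whether agility, perceived exertion and fatigue resistance differs between N0, N25, and N45 conditions". It then lists Pro Agility time, the RSA metrics and RPE under secondary objectives. The abstract (section 1) and section 7.1 name Pro Agility time as the one primary outcome. Section 7.2 places RSA (with its fatigue index) and RPE among the secondary outcomes.

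On analysis, the hypotheses in sections 1 and 2 are that one or both nap conditions do better than no nap. Section 13 plans RM-ANOVA across the three conditions, Bonferroni adjustment where appropriate, Cohen's dz for pairs and 95% CIs. It gives no equivalence or non-superiority margin. It also states: "Pre-specified sensitivity checks reported", without naming the checks.

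**The concern.** Three things meet here, and each affects what the trial may conclude.

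- **Timing.** A plan shows pre-specification by being dated before the results. One whose title already gives the direction of three outcomes cannot do that unaided, so any confirmatory label needs an earlier dated version behind it.
- **Hierarchy.** With two incompatible rankings in one document, a reader cannot tell whether the trial stands or falls on one test or on three. A finding on exertion or fatigue is primary under section 2 and secondary under sections 1 and 7.
- **Negative conclusion.** A test of difference that fails to reach significance does not show that improvement is absent. In a sample of 16 the data may be compatible with a worthwhile benefit, and coaches or later researchers would read the title as having ruled one out.

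**Working it through.** **1. Outcome ranking, side by side**

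| Outcome | Section 1 | Section 2 | Section 7 |
|---|---|---|---|
| Agility / Pro Agility time | primary | primary objective and secondary objective | primary (7.1) |
| Exertion (RPE) | secondary | primary objective and secondary objective | secondary (7.2) |
| Fatigue (RSA fatigue index) | secondary, under RSA | primary objective and secondary objective | secondary (7.2) |

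Sections 1 and 7 agree. Section 13 fits them, since it puts RSA and RPE under secondary analyses. Section 2 is the outlier, and it places all three outcomes in both tiers.

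**2. Dates.** Read as 5 March or 3 May 2024, the ethics date is at least 12 months before 10 May 2025. Section 17 puts ethics approval in months 0–1, data collection in months 2–3 and reporting in months 4–5. That is a planned timetable, not a record of when the sessions took place.

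**3. The plan's own sample size.** Inputs from section 8: α = 0.05, power 0.80, f = 0.30–0.40, m = 3 conditions. Not given, so assumed: correlation between conditions ρ = 0.5 and sphericity ε = 1. Then λ = f²·N·m/(1−ρ), with df 2 and 2(N−1).

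- f = 0.40, N = 12: λ = 0.16 × 12 × 3/0.5 = 11.52, power 0.816. The stated minimum of 12 is reproduced.
- f = 0.30, N = 16: λ = 0.09 × 16 × 3/0.5 = 8.64, power 0.706. Over ρ = 0 to 0.8 this ranges from 0.41 to 0.98.

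This is a calculation for detecting a difference. It names no outcome and says nothing about showing that improvement is absent.

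**4. What 16 players can say about one pair of conditions.** Work in dz, the mean difference divided by the SD of the differences; these results do not depend on ρ. Bonferroni is taken over the three pairs (an assumption, as section 13 does not fix the number), so α = 0.05/3 = 0.0167.

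- CI half-width = t(15)/√16. Unadjusted: 2.131/4 = 0.533. Bonferroni: 2.694/4 = 0.673.
- dz detectable with 80% power (noncentral t, 15 df): 0.75 unadjusted, 0.90 with Bonferroni.
- Chance of a non-significant result at an assumed true dz:

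| True dz | Unadjusted | Bonferroni |
|---|---|---|
| 0.3 | 1 − 0.203 = 80% | 1 − 0.096 = 90% |
| 0.5 | 1 − 0.465 = 54% | 1 − 0.280 = 72% |
| 0.8 | 1 − 0.848 = 15% | 1 − 0.690 = 31% |

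**5. The weaker, one-sided claim.** Suppose the true difference is zero and the claim is only that any benefit is smaller than a margin. The margins below are assumed, because the protocol gives none.

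| Margin (dz) | Power, two-sided 95% CI (one-sided 0.025) | Power, one-sided 0.05 |
|---|---|---|
| 0.3 | 20% | 31% |
| 0.5 | 46% | 60% |
| 0.8 | 85% | 92% |

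For 80% power with the 95% CI, about 90 players are needed at a margin of 0.3 and 34 at 0.5. With one-sided 0.05 the numbers are 71 and 27.

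**The case against.** The best defence is that the body of the protocol makes no null claim. Its hypothesis is superiority, it plans effect sizes and 95% CIs, and only the title says more. The title says that fatigue resistance is not improved, which is weaker than no effect. The results are not shown, and an estimate on the unfavourable side could have a CI that excludes any useful benefit. All of this is fair. It makes the conclusion conditional, but it does not supply the missing margin, and the one-sided reading in step 5 is also poorly powered unless the margin is large.

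Some stronger readings are tempting but not supported:

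- **That the outcomes were ranked after the results were known.** Section 2's primary objective names the same three constructs as the title, which invites this. The documents do not show it: a manuscript title may have been put on an older plan, and parts of sections 12 and 16 are still written prospectively.
- **That the whole text was written after the data.** The enrolment figure and the chronotype statement are not outcome results. MEQ is taken once at baseline, so both fit an update made before any nap session.
- **That subgroups are wrongly called pre-specified.** Section 13 says there are none. The only positive use of the label is for the sensitivity checks.

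**Conclusion.** The point holds in three limited parts. The title states results, so this document alone cannot establish what was fixed in advance. Section 2 contradicts sections 1 and 7 on the primary outcome. The title's negative statement on fatigue has no planned analysis that could support it.

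The missing margin is the main reason for the third part, and the sample size adds to it: a pairwise 95% CI extends about 0.53 SD of the differences either side of the estimate, or 0.67 with Bonferroni. The CI widths and detectable effects rest on n = 16 completers and, where stated, three pairwise comparisons. The miss rates rest on assumed true effects, and the figures in step 5 on assumed margins. A separate SAP or an earlier dated version could settle the timing question, but would not remove the contradiction inside this protocol.

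**What to change.** - Give the protocol a neutral title that names the comparison and not the findings.
- Rewrite section 2 to match sections 1 and 7: Pro Agility time as the single confirmatory outcome, RPE and the fatigue index as secondary, and no outcome in two tiers.
- Cite the dated original version. In section 13, keep the pre-specified label for sensitivity checks only where that version contains them, and name them.
- Report the fatigue index as N25-minus-N0 and N45-minus-N0 differences with 95% CIs. Describe a non-significant result as no difference detected. Claim absence of improvement only if the CI excludes a benefit larger than a margin justified on external grounds.

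The cost is wording in the title and in sections 2 and 13, plus locating the earlier version; no new data are needed. The price is more cautious conclusions on exertion and fatigue.

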### 2. Objectives and Testable Hypotheses

**Primary objective:** Determine whether agility, perceived exertion and fatigue resistance differs between N0, N25, and N45 conditions.

**Primary hypothesis:** N25 and/or N45 conditions gives better results than N0.

**Secondary objectives:** Assess condition effects on Pro Agility time, RSA metrics (best/mean time, fatigue index), RPE, Hooper Index, and VAS alertness/sleep quality.

**Exploratory objectives:** Examine associations between PSQI/POMS and performance/subjective outcomes.

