## 7. Outcomes and Assessment Schedule

### 7.1 Primary Outcome

- **Pro Agility Test time (20-yard shuttle, total 18.28 m):** Provided agility outcomes [14].

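### Section 2 sets a three-construct primary objective, while the abstract and Section 7.1 name Pro Agility time as the only primary outcome

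*Protocol*

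**What the plan says.** Section 2 gives the primary objective as "Determine whether agility, perceived exertion and fatigue resistance differs between N0, N25, and N45 conditions" and the primary hypothesis as "N25 and/or N45 conditions gives better results than N0". Its secondary objectives follow: "Assess condition effects on Pro Agility time, RSA metrics (best/mean time, fatigue index), RPE, Hooper Index, and VAS alertness/sleep quality".

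The structured abstract differs. Its objective reads "Primary objective is to test whether nap conditions improve pro-agility performance", its hypothesis "Hypothesis: N25 and/or N45 outperform N0 on pro-agility time" and its outcome list "Primary: Pro Agility Test time". Its secondary objectives leave agility out: "Secondary objectives examine effects on RSA, RPE, Hooper wellness, and VAS alertness/sleep quality". Section 7.1 lists one primary outcome, "Pro Agility Test time (20-yard shuttle, total 18.28 m".

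Section 7.2 places RSA (with its fatigue index) and session-mean RPE among the secondary outcomes, and Section 13 analyses both as secondary. The primary analysis in Section 13 is a repeated-measures ANOVA over the three conditions. It names no outcome, and it mentions Bonferroni without defining the family it covers.

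**The concern.** The protocol holds two outcome hierarchies and no order of precedence between them. Under Section 2, a primary claim could rest on agility, on perceived exertion or on a fatigue measure that is not identified. Under the abstract and Section 7.1, it can rest only on Pro Agility time.

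Section 2 also conflicts with itself, because agility and perceived exertion appear at both the primary and the secondary level. Fatigue resistance does too if it means the RSA fatigue index, which is likely but not stated.

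The document's title already states findings on the same three constructs: agility better, exertion lower, fatigue resistance not improved. That does not show that the hierarchy was changed. It does mean that anyone who settles the conflict now does so with results in view.

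**Working it through.** **The statements side by side**

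| Place in protocol | Agility | Perceived exertion | Fatigue resistance / RSA fatigue index |
|---|---|---|---|
| Abstract | primary (objective, hypothesis, outcome list) | secondary | RSA secondary |
| Section 2, primary objective | primary | primary | primary, endpoint not defined |
| Section 2, secondary objectives | secondary | secondary | fatigue index secondary |
| Section 7.1 | primary | – | – |
| Section 7.2 | – | secondary | secondary |
| Section 13 | outcome of primary analysis not named | secondary | secondary |

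The contradiction is complete on the text and depends on no figure.

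**False-positive consequence**

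Input: α = 0.05 (Section 8). Assumption: any one construct suffices and each is tested unadjusted. The protocol states neither an any/all rule nor an adjustment across outcomes.

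- One primary outcome: 0.05.
- Two constructs with a clear endpoint (Pro Agility time, mean RPE), independent: 1 − 0.95² = 0.0975; upper bound under any dependence 2 × 0.05 = 0.10.
- Three constructs, with one fatigue measure, independent: 1 − 0.95³ = 0.1426; upper bound 3 × 0.05 = 0.15.
- All three must succeed: at most 0.05.

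The outcomes come from the same players and are probably correlated. The protocol gives no correlation, so a range was simulated: 200,000 null trials, n = 16, three conditions, F(2,30) at 0.05, sphericity, equal between-outcome correlation r.

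| r | any of 2 | any of 3 |
|---|---|---|
| 0 | 9.8% | 14.3% |
| 0.3 | 9.5% | 13.7% |
| 0.5 | 9.2% | 12.8% |
| 0.7 | 8.6% | 11.3% |
| 0.8 | 8.1% | 10.2% |

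**Sample-size consequence**

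Inputs from Section 8: three within-subject conditions, power 0.80, f = 0.30–0.40, minimum of 12, 16 recruited. The correlation between conditions is not stated; ρ = 0.5 is assumed. Noncentrality λ = N·3·f²/(1 − ρ), with 2 and 2(N − 1) degrees of freedom.

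- Reproducing the plan's figure: f = 0.40, N = 12 gives λ = 12 × 3 × 0.16/0.5 = 11.52 and power 0.816. The stated minimum of 12 is reproduced.
- At α = 0.05/3 for three primaries, the N per endpoint at f = 0.40 rises from 12 to 16 (power 0.829 at n = 16).
- At f = 0.30 it rises from 20 to 26. Power at n = 16 (λ = 16 × 3 × 0.09/0.5 = 8.64) falls from 0.706 to 0.526.

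The choice of hierarchy therefore also bears on whether 16 players are enough.

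**The case against.** The best reply is that the working hierarchy is clear despite Section 2. The abstract names Pro Agility in three places, Section 7.1 defines it alone as primary, and Sections 7.2 and 13 are consistent with that. On this view Section 2 is loosely worded and nothing more. It probably is the outlier, but no passage says which section governs, and it is the section that formally states the hypotheses. Nor can it be read as a deliberately broad objective, because the abstract's objective is limited to pro-agility performance and Section 2 repeats its own components as secondary.

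The error rates are also open to challenge, in three ways:

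- **Any/all rule.** Section 2 joins the constructs with a conjunction, which may mean that all must succeed. The error is then at most 5%.
- **Bonferroni.** The abstract and Section 13 both mention it, so testing may not be wholly unadjusted. The family is not defined, and it may cover only the pairwise condition comparisons.
- **Direction.** The hypothesis is directional, whereas the rates count any omnibus rejection. By symmetry N0 ranks best in one third of null rejections, so a false claim of benefit occurs at most 0.05 × 2/3 = 3.3% of the time for one outcome and 1 − (1 − 0.0333)³ ≈ 9.7% for any of three independent outcomes.

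These points stand as limits on the size. The directional version roughly triples the error, as the omnibus version does (5% to 14.3%), and none of the three touches the contradiction in the text.

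Finally, the ethics-approved text is not available to this review, so what it held is unknown. The sponsor has it and can check.

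**Conclusion.** The concern holds. Section 2 contradicts the abstract and Section 7.1 on the primary outcome, and contradicts itself by placing agility and perceived exertion at both levels. Nothing elsewhere in the protocol resolves this.

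The size is conditional. If any one of three constructs could carry a primary claim without adjustment, the false-positive risk would be about 10% to 14% over between-outcome correlations from 0.8 down to 0, and at most 15%. It is at most 5% if Section 7.1 governs or if all three must succeed. The any-one rule, the lack of adjustment and the correlations are assumptions; the textual conflict is not. It must be fixed, because it decides which result may support a primary claim in a document whose title already states results.

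**What to change.** First check which hierarchy the ethics-approved version held (approval dated 05/03/2024; this document is dated 10 May 2025).

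- **If Pro Agility time was the sole primary outcome:** reword the objective and hypothesis in Section 2 to match the abstract and Section 7.1. Remove Pro Agility time from the secondary objectives, and keep RPE and the RSA metrics, including the fatigue index, as secondary.
- **If the approved hierarchy differed:** report that hierarchy, and disclose the change and its date.
- **If three primary outcomes were approved:** also name the endpoint for fatigue resistance, and state whether any or all must succeed with the matching control of α.

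In each case, name the primary outcome in the primary analysis of Section 13.

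The cost is one document check and a few reworded lines. Under the single-primary hierarchy, RPE and fatigue results cannot be presented as primary claims. If the approved version differed, the change has to be declared as made after approval.

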### 3. Study Design

- **Design:** Quasi-experimental, repeated-measures crossover.
- **Conditions:** N0 (no nap), N25 (25 min), N45 (45 min).
- **Order:** Randomized within participant.
- **Washout:** 48 h between sessions [1].
- **Timing:** Nap starts at 14:00; testing begins 60 min post-awakening [2,3].
- **Testing flow:** Warm-up → Pro Agility → 3-min rest → RSA; RPE after each sprint.

### 4. Setting and Infrastructure

- **Sleep environment:** Isolated, ventilated, dark rooms with blackout curtains; ambient temperature  $\approx 22^{\circ}\text{C}$  [4].
- **Sleep monitoring:** Visual Analogue Scale for sleep–wake verification [5,6].
- **Physiological monitoring:** Polar H10 for heart rate during warm-up [7].

## 5. Participants

### 5.1 Inclusion Criteria

- Competitive male players from Yeni Malatyaspor U17 or U19 squads.
- Healthy, no recent illness or injury.
- No habitual daytime napping.

### 5.2 Exclusion Criteria

- Active infection.
- Diagnosed hyperactivity or sleep disorder.
- Experiencing sleep problems on protocol days.
- Non-adherence to instructions, inability to complete sessions, or cooperation issues.

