### 5.3 Sampling and Screening

- End-of-season volunteer recruitment from U17–U19 squads.
- Pre-screening by trained staff; verification with training logs.

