## 6. Interventions

- **Conditions:** N0, N25, N45.
- **Nap procedure:** 10-min room adaptation at 13:50 [8]; nap opportunity at 14:00; preferred lying position allowed.
- **Verification:** Sleep onset, duration, and awakening verified via Visual Analogue Scale; wakefulness confirmed in N0 [5,6].
- **Pre-session standards:** Avoid strenuous training for 24 h; avoid alcohol for 24 h and caffeine for 6 h; verbal compliance check at arrival [9–11].
- **Prohibited activities:** No phone use, video games, or visually stimulating tasks during all conditions [12,13].
- **Warm-up standardization:** Light jogging plus a 3-min mobility sequence; heart rate monitored with Polar H10 [7].
- **Testing order:** Pro Agility → 3-min rest → RSA; RPE recorded after each sprint.

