## 9. Randomization, Allocation Concealment, and Blinding

- **Randomization:** Within-subject random assignment of condition order.
- **Allocation concealment:** Condition order not disclosed to participants until session day; administered by study staff.
- **Blinding:** Participant blinding is infeasible; automated timing reduces measurement bias; assessor blinding not implemented.
- **Unblinding:** Not applicable.

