## 10. Study Workflow and Procedures

1. **Screening and baseline:** Eligibility, informed consent, demographics and anthropometry (SECA stadiometer; Toledo 2096 PP scale;  $\text{BMI}=\text{kg}/\text{m}^2$  [27]). MEQ, PSQI, POMS administered once at baseline [20–22,28].
2. **Pre-session standards:** 24 h no heavy training; 24 h no alcohol; 6 h no caffeine; verbal verification at arrival [9,11,29].
3. **Nap session:** 13:50 adaptation; 14:00 N0/N25/N45; dark quiet room  $\approx 22^\circ\text{C}$ ; subjective verification [5,6]; prohibition of visual/stimulating activities [12,13].
4. **Warm-up:** Light jog plus 3-min mobility; heart rate monitored with Polar H10 for standardization [7].
5. **Performance tests:** 60 min post-awakening [2,3], Pro Agility  $\rightarrow$  3-min rest  $\rightarrow$  RSA (6×30 m, 20-s intervals [15–17]); RPE after each sprint [18].
6. **Post-session:** Hooper and VAS forms [8,19].

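### Section 5.2 excludes the player for events that arise only at his sessions; followed through the RM-ANOVA of Section 13, this would discard his other valid sessions, and no passage prevents it.

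*Protocol*

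**What the plan says.** Section 5.2 of the Protocol is one list of exclusion criteria. Active infection and a diagnosed disorder can be established at entry. Beside them stand "Experiencing sleep problems on protocol days" and "Non-adherence to instructions, inability to complete sessions, or cooperation issues".

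Other sections show when these events become known:

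- Section 5.3 (screening): "Pre-screening by trained staff; verification with training logs".
- Section 10, step 2 (before each session): "24 h no heavy training; 24 h no alcohol; 6 h no caffeine; verbal verification at arrival".
- Section 6 (during the session): "No phone use, video games, or visually stimulating tasks during all conditions".
- Section 9 (condition order): "Condition order not disclosed to participants until session day; administered by study staff".

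The primary analysis in Section 13 is "RM-ANOVA across N0–N25–N45; Bonferroni where appropriate". The same section has a line on missing data and sensitivity, "Pre-specified sensitivity checks reported", without naming the checks. Section 12 permits multiple imputation but does not require it. Section 8 recruits 16 players against a minimum of 12, partly to allow for attrition. Section 17 plans three sessions per player.

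**The concern.** An exclusion criterion normally decides who enters a trial. Several items in Section 5.2 can be met only after a player has entered, and possibly after he has completed one or two sessions. If he is then excluded as a player, up to two valid sessions go with the affected one. The trial has only 16 × 3 = 48 planned sessions.

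Three things are at stake:

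- **Power**, because valid within-player comparisons are lost.
- **Scope**, because the result would describe only players who complied and completed.
- **Bias**, which is possible if exclusion depends on both condition and performance. Assessors are not blinded (Section 9), and the protocol does not say who decides an exclusion.

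**Working it through.** **1. Which items are session-day events?** A sleep problem on a protocol day cannot be known before that day. The training, alcohol and caffeine rules are checked at arrival, and the ban on phones and visual tasks applies during the conditions. Actual failure to complete a session is seen only at the session. Cooperation, or a foreseeable inability to attend, could be judged at pre-screening. The order appears to be set by the session day, since Section 9 withholds it until then, but the protocol does not date its generation.

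**2. Does any passage keep the player's recorded sessions?** Sections 8, 12 and 13 are the candidates. The attrition allowance, the optional imputation and the sensitivity checks are all silent on players excluded under Section 5.2. No passage provides for repeating a session or for analysing all randomised players.

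**3. Inputs for the size.** From Section 8: alpha 0.05, target power 0.80, f = 0.30 to 0.40, minimum 12, recruited 16. Assumed, because the protocol gives no value: within-player correlation rho = 0.5 (0.3 and 0.7 also tried), sphericity, and the number of affected players k.

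**4. Reproducing the plan's figure.** For n players with three sessions each, lambda = 3·n·f²/(1 − rho), with 2 and 2(n − 1) degrees of freedom. At f = 0.40 and n = 12, lambda = 3 × 12 × 0.16/0.5 = 11.52 and power is 0.816, so the minimum of 12 reproduces at the top of the stated range. With all 16 players, power is 0.926 at f = 0.40. At f = 0.30, lambda = 3 × 16 × 0.09/0.5 = 8.64 and power is 0.706.

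**5. Completers against remaining sessions.** Suppose each of k players loses one session. The completer analysis uses 16 − k players in the formula above. The alternative uses all 48 − k remaining sessions: generalised least squares with a random player intercept and 48 − k − 16 − 2 = 30 − k denominator degrees of freedom. It was evaluated over every allocation of the lost sessions to conditions and five patterns of means scaled to f. Results at rho = 0.5:

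| k | f | Completers | Remaining sessions, mean (range) |
|---|---|---|---|
| 1 | 0.30 | 0.673 | 0.691 (0.678–0.705) |
| 2 | 0.30 | 0.637 | 0.676 (0.647–0.703) |
| 3 | 0.30 | 0.598 | 0.660 (0.614–0.701) |
| 4 | 0.30 | 0.557 | 0.643 (0.579–0.699) |
| 4 | 0.40 | 0.816 | 0.885 (0.836–0.921) |

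For k = 4 the comparison is 36 sessions against 44. With k = 4, f = 0.30 and losses spread over the conditions, rho = 0.3 gives 0.419 against 0.498, and rho = 0.7 gives 0.789 against 0.862.

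**6. How many completers?** Assume each session independently carries a chance p of an event. A player then completes with probability (1 − p)³.

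- p = 0.05: 0.857; 16 × 0.857 = 13.7 completers expected; chance of fewer than 12 is 7%.
- p = 0.10: 0.729; 16 × 0.729 = 11.7 expected; chance of fewer than 12 is 45%.

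**7. If affected sessions are run and kept.** Step 5 prices a session that is missing or left out. Keeping a non-adherent session is different. A simulation (40,000 trials, rho = 0.5, f = 0.30, evenly spaced means, k = 4) compared all 48 sessions with completers:

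- No dilution: 0.71 against 0.56.
- Affected sessions behave like N0: 0.61 against 0.56.
- The same, and 1.5 times as noisy: about 0.57 against 0.55.

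With k = 2, the last case shows essentially no gain.

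**8. Bias.** In simulations with no true effect (20,000 trials each, n = 16, total variance 1, rho = 0.5), exclusion that depended on condition alone (N0 20%, naps 5%) gave a bias of 0.00 SD. Exclusion of slow sessions equally in all conditions gave about 0. Exclusion triggered by slow sessions in one condition only, at 20, 30 or 40% against 5%, gave 0.04, 0.06 and 0.09 SD, with type I error of 5.0 to 6.1%.

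**The case against.** The strongest reply is that the protocol never says recorded data are discarded or that only complete cases are analysed. Section 13 defines no analysis set, and a separate statistical analysis plan may do so. Sections 8, 12 and 13 expect some incomplete players. Part of the quoted item can be judged at screening. This stands to the following extent: a reader might infer that the protocol prescribes a completers-only primary analysis, and the text does not support that. It is the most natural consequence of applying Section 5.2, not a stated rule. What is stated is that session-day events exclude the player. An analysis plan that kept him would have to depart from that rule, so the point is more than a detail left for later.

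A second reply is that the gain is small and the power figures do not fit the main remedy. This also stands in part. The gain is 0.02 for one player and 0.04 for two, and it reaches about 0.09 only when a quarter of the sample is affected. Those figures price an omitted or missing session. For non-adherent sessions that are kept, the gain runs from almost nothing to more than stated, depending on dilution.

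A third reply is that an adherent-only question is legitimate in a short crossover. It is, but it calls for leaving out the affected session, not the player.

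**Conclusion.** The point holds as a fault in how the rule is written. Section 5.2 turns session-day events into exclusions of the player, and nothing in Sections 8, 12 or 13 stops that from removing his valid sessions from the primary analysis. It should be corrected.

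The cost is small to moderate and conditional. No event rate is documented, rho = 0.5 is assumed, and without events nothing is lost. When the affected session is missing or omitted, analysing the rest was never worse than completers in the cases examined.

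A reader might also infer that the nap comparisons are biased, or that players were in fact dropped. The protocol supports neither. It reports no number of exclusions. Bias needs exclusion to depend on both condition and performance, and in the illustrations it was at most 0.09 SD.

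**What to change.** - **Section 5.2:** keep only facts known before the condition order is assigned. Record session-day sleep problems, non-adherence and non-completion as session-level deviations. This concerns who is analysed, not whether a session should go ahead.
- **Section 13:** make the primary analysis a linear mixed model with a random participant effect and small-sample degrees of freedom, on the recorded sessions of all randomised players, by assigned condition. Report adherent completers as a sensitivity analysis.
- **If an adherent-only question is preferred:** say so, and omit the affected session, not the player.
- **Sections 8 and 12:** state how the attrition allowance and any imputation relate to these events.

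The cost is wording in four sections, with no extra data. There are two drawbacks. Poorly adherent sessions kept in the analysis may dilute the effect, and the mixed model gives no protection if sessions are missing because of their own unobserved result.
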